17.7 Survival

Survival will be measured from the date of enrollment.

18.0 COSTS TO THE SUBJECT

There will be no additional costs to subjects as a result of being in this study. Merck will provide the study drug pembrolizumab free of charge. The research specific blood and tissue testing will also be done at no charge to the subject.

Routine medical care given for the disease under study (which is care a subject would receive whether or not they were in this study), such as the standard chemotherapy drugs and surgery, will be charged to subject's insurance company.

19.0 STUDY ASSESSMENTS

19.1 Medical History

A medical history will be obtained by the investigator or qualified designee. Medical history will include all active conditions, and any condition diagnosed within the prior 10 years that are considered to be clinically significant by the Investigator. Details regarding the disease for which the subject has enrolled in this study will be recorded separately and not listed as medical history.

19.2 Prior and Concomitant Medications Review

19.2.1 Prior Medications

The investigator or qualified designee will review prior medication use, including any protocol-specified washout requirement, and record prior medication taken by the subject within 28 days before starting the trial. Treatment for the disease for which the subject has enrolled in this study will be recorded separately and not listed as a prior medication.

19.2.2 Concomitant Medications

The investigator or qualified designee will record medication, if any, taken by the subject during the trial. All medications related to reportable SAEs and ECIs should be recorded as defined in Section 20.51.

19.3 Disease Details and Treatments

19.3.1 Disease Details

The investigator or qualified designee will obtain prior and current details regarding disease status.

19.3.2 Prior Treatment Details

The investigator or qualified designee will review all prior cancer treatments including systemic treatments, radiation and surgeries.

19.3.3 Subsequent Anti-Cancer Therapy Status

The investigator or qualified designee will review all new anti-neoplastic therapy initiated after the last dose of trial treatment. If a subject initiates a new anti-cancer therapy within 30 days after the last dose of trial treatment, the 30-day Safety Follow-up visit must occur before the first dose of the

new therapy. Once new anti-cancer therapy has been initiated the subject will move into survival follow-up.

19.4 Adverse Event (AE) Monitoring

The investigator or qualified designee will assess each subject to evaluate for potential new or worsening AEs as specified in the Study Schedule (Appendix A) and more frequently if clinically indicated. Adverse experiences will be graded and recorded throughout the study and during the follow-up period according to NCI CTCAE Version 4.0 (see Section 20.0). Toxicities will be characterized in terms regarding seriousness, causality, toxicity grading, and action taken with regard to trial treatment.

For subjects receiving treatment with pembrolizumab all AEs of unknown etiology associated with pembrolizumab exposure should be evaluated to determine if it is possibly an event of clinical interest (ECI) of a potentially immunologic etiology (termed immune-related adverse events, or irAEs). Please refer to section 20 for detailed information regarding the assessment and recording of AEs.

19.5 Full Physical Exam

The investigator or qualified designee will perform a complete physical exam during the screening period. Clinically significant abnormal findings should be recorded as medical history. A full physical exam should be performed during screening.

19.5.1 Directed Physical Exam

For cycles that do not require a full physical exam per Study Schedule- Appendix A, the investigator or qualified designee will perform a directed physical exam as clinically indicated prior to trial treatment administration.

19.6 Vital Signs

The investigator or qualified designee will take vital signs at screening, prior to the administration of each dose of trial treatment and at treatment discontinuation as specified in the Study Calendar (Appendix A). Vital signs should include temperature, pulse, respiratory rate, weight and blood pressure. Height will be measured at screening only.

19.7 Laboratory Procedures/Assessments

Details regarding specific laboratory procedures/assessments to be performed in this trial are provided below. Laboratory Safety Evaluations (Hematology, Chemistry and Urinalysis and others) are specified in Table 5 (below).

Table 5- Laboratory Tests

Hematology	Chemistry	Urinalysis	Other
Hematocrit	Albumin	Blood	Serum β -human chorionic gonadotropin†
Hemoglobin	Alkaline phosphatase	Glucose	(β -hCG)†
Platelet count	Alanine aminotransferase (ALT)	Protein	PT (INR)
WBC (total and differential)	Aspartate aminotransferase (AST)	Specific gravity	aPTT
Red Blood Cell Count	Lactate dehydrogenase (LDH)	Microscopic exam (If abnormal)	Total triiodothyronine (T3)
Absolute Neutrophil Count	Carbon Dioxide ‡ (CO₂ or bicarbonate)	results are noted	Free thyroxine (T4)
Absolute Lymphocyte Count	Uric Acid		Thyroid stimulating hormone (TSH)
	Calcium		
	Chloride		Blood for correlative studies
	Glucose		
	Phosphorus		
	Potassium		
	Sodium		
	Magnesium		
	Total Bilirubin		
	Direct Bilirubin (If total bilirubin is elevated above the upper limit of normal)		
	Total protein		
	Blood Urea Nitrogen		
† Perform on women of childbearing potential only. ‡ If considered standard of care in your region.			

20.0 SAFETY

All patients who receive at least one dose of pembrolizumab will be considered evaluable for safety parameters. Additionally, any occurrence of a non-SAE or SAE from time of consent forward, up to and including follow-up visits, will be reported as per Adverse Event Reporting sections below. Safety will be evaluated for all treated patients using the National Cancer Institute (NCI) Common Terminology Criteria for Adverse Events (CTCAE), Version 4.0 (<http://ctep.cancer.gov>). Safety assessments will be based on medical review of adverse event reports and the results of vital sign measurements, physical examinations, and clinical laboratory tests.

20.1 Safety Monitoring and Reporting

The PI at each institution is responsible for the identification and documentation of adverse events and serious adverse events, as defined below. At each study visit, the PI or designee must assess, through non-suggestive inquiries of the subject or evaluation of study assessments, whether an AE or SAE has occurred. Adverse events that are judged to be Serious Adverse Events by the institutional PI should be reported to the Duke Cancer Institute Safety Desk as outlined in Appendix K- Reporting Procedures for Adverse Events and Serious Adverse Events by Participating Sites.

20.2 Assessing and Recording Adverse Events

An adverse event is defined as any untoward medical occurrence in a patient or clinical investigation subject administered a pharmaceutical product and which does not necessarily have to have a causal relationship with this treatment. An adverse event can therefore be any unfavorable and unintended sign (including an abnormal laboratory finding, for example), symptom, or disease temporally associated with the use of a medicinal product or protocol-specified procedure, whether or not considered related to the medicinal product or protocol-specified procedure. Any worsening (i.e., any clinically significant adverse change in frequency and/or intensity) of a preexisting condition that is temporally associated with the use of the Merck's product, is also an adverse event.

Changes resulting from normal growth and development that do not vary significantly in frequency or severity from expected levels are not to be considered adverse events. Examples of this may include, but are not limited to, teething, typical crying in infants and children and onset of menses or menopause occurring at a physiologically appropriate time.

Merck product includes any pharmaceutical product, biological product, device, diagnostic agent or protocol-specified procedure, whether investigational (including placebo or active comparator medication) or marketed, manufactured by, licensed by, provided by or distributed by Merck for human use.

Adverse events may occur during the course of the use of Merck product in clinical trials, or as prescribed in clinical practice, from overdose (whether accidental or intentional), from abuse and from withdrawal.

Progression of the cancer under study is not considered an adverse event.

All adverse events that occur after the consent form is signed but before treatment allocation/randomization must be reported by the investigator if they cause the subject to be excluded from the trial, or are the result of a protocol-specified intervention, including but not limited to washout or discontinuation of usual therapy, diet, placebo treatment or a procedure.

From the time of treatment allocation/randomization through 30 days following cessation of treatment, all adverse events must be reported by the investigator. Such events will be recorded at each examination on the Adverse Event case report forms/worksheets. The reporting timeframe for adverse events meeting any serious criteria is described in section 20.5.1 & 20.6. The investigator will make every attempt to follow all subjects with non-serious adverse events for outcome.

Adverse events will not be collected for subjects during the pre-screening period (for determination of archival tissue status) as long as that subject has not undergone any protocol-specified procedure or intervention. If the subject requires a blood draw, fresh tumor biopsy etc., the subject is first required to provide consent to the main study and AEs will be captured according to guidelines for standard AE reporting.

20.3 Definition of an Overdose for This Protocol & Reporting to Sponsor and to Merck

For purposes of this trial, an overdose of pembrolizumab will be defined as any dose of 1,000 mg or greater (≥ 5 times the indicated dose). No specific information is available on the treatment of overdose of pembrolizumab. Appropriate supportive treatment should be provided if clinically indicated. In the event of overdose, the subject should be observed closely for signs of toxicity. Appropriate supportive treatment should be provided if clinically indicated.

If an adverse event(s) is associated with (“results from”) the overdose of a Merck product, the adverse event(s) is reported as a serious adverse event, even if no other seriousness criteria are met.

If a dose of Merck’s product meeting the protocol definition of overdose is taken without any associated clinical symptoms or abnormal laboratory results, the overdose is reported as a non-serious Event of Clinical Interest (ECI), using the terminology “accidental or intentional overdose without adverse effect.”

All reports of overdose with and without an adverse event must be reported within 24 hours to the Duke Sponsor (DCI Safety Desk) who will report within 2 working days to Merck Global Safety. (Attn: Worldwide Product Safety; [contact])

20.4 Reporting of Pregnancy and Lactation to the Sponsor and to Merck

Although pregnancy and lactation are not considered adverse events, it is the responsibility of investigators or their designees to report any pregnancy or lactation in a subject (spontaneously reported to them) that occurs during the trial.

Pregnancies and lactations that occur after the consent form is signed but before treatment allocation/randomization must be reported by the investigator if they cause the subject to be excluded from the trial, or are the result of a protocol-specified intervention, including but not limited to washout or discontinuation of usual therapy, diet, placebo treatment or a procedure.

Pregnancies and lactations that occur from the time of treatment allocation/randomization through 120 days following cessation of Sponsor's product, or 30 days following cessation of treatment if the subject initiates new anticancer therapy, whichever is earlier, must be reported by the investigator. All reported pregnancies must be followed to the completion/termination of the pregnancy. Pregnancy outcomes of spontaneous abortion, missed abortion, benign hydatidiform mole, blighted ovum, fetal death, intrauterine death, miscarriage and stillbirth must be reported as serious events (Important Medical Events). If the pregnancy continues to term, the outcome (health of infant) must also be reported.

Such events must be reported within 24 hours to the Duke Sponsor (DCI Safety Desk) who will report within 2 working days to Merck Global Safety. (Attn: Worldwide Product Safety; [contact])

20.5 Immediate Reporting of Serious Adverse Events

20.5.1 Serious Adverse Events

A serious adverse event is any adverse event occurring at any dose or during any use of Merck's product that:

- Results in death;
- Is life threatening;
- Results in persistent or significant disability/incapacity;
- Results in or prolongs an existing inpatient hospitalization;
- Is a congenital anomaly/birth defect;
- Is another important medical event
- **Note:** In addition to the above criteria, adverse events meeting either of the below criteria, although not serious per ICH definition, are reportable to the Merck in the same timeframe as SAEs to meet certain local requirements. Therefore, these events are considered serious by Merck for collection purposes.

- Is a new cancer (that is not a condition of the study);
- Is associated with an overdose.

Refer to Table 6 for additional details regarding each of the above criteria.

For the time period beginning when the consent form is signed until treatment allocation/randomization, any serious adverse event, or follow up to a serious adverse event, including death due to any cause other than progression of the cancer under study that occurs to any subject must be reported within 24 hours to the Duke Sponsor (DCI Safety Desk) who will report within 2 working days to Merck Global Safety if it causes the subject to be excluded from the trial, or is the result of a protocol-specified intervention, including, but not limited to, washout or discontinuation of usual therapy, diet, placebo treatment or a procedure.

For the time period beginning at treatment allocation/randomization through 90 days following cessation of treatment, or 30 days following cessation of treatment if the subject initiates new anticancer therapy, whichever is earlier, any serious adverse event, or follow up to a serious adverse event, including death due to any cause other than progression of the cancer under study whether or not related to the Merck product, must be reported within 24 hours to the Duke Sponsor (DCI Safety Desk) who will report within 2 working days to Merck Global Safety.

Additionally, any serious adverse event, considered by an investigator who is a qualified physician to be related to Merck product that is brought to the attention of the investigator at any time following consent through the end of the specified safety follow-up period specified in the paragraph above, or at any time outside of the time period specified in the previous paragraph also must be reported immediately to the Duke Sponsor and to Merck Global Safety.

All subjects with serious adverse events must be followed up for outcome.

SAE reports and any other relevant safety information are to be forwarded to the DCI Safety Desk for forwarding to Merck Global Safety [contact]

A copy of all 15 Day Reports and Annual Progress Reports are submitted as required by FDA, European Union (EU), Pharmaceutical and Medical Devices agency (PMDA) or other local regulators. Investigators will cross reference this submission according to local regulations to the Merck Investigational Compound Number (IND, CSA, etc.) at the time of submission. Additionally, investigators will submit a copy of these reports to Merck & Co., Inc. (Attn: Worldwide Product Safety; [contact]) at the time of submission to FDA.

20.6 Events of Clinical Interest

Selected non-serious and serious adverse events are also known as Events of Clinical Interest (ECI) and must be reported within 24 hours to the Duke Sponsor (DCI Safety Desk) who will report within 2 working days to Merck Global Safety. (Attn: Worldwide Product Safety; [contact]).

For the time period beginning when the consent form is signed until treatment allocation/randomization, any ECI, or follow up to an ECI, that occurs to any subject must be reported within 24 hours to the Sponsor and within 2 working days to Merck Global Safety if it causes the subject to be excluded from the trial, or is the result of a protocol-specified intervention, including but not limited to washout or discontinuation of usual therapy, diet, placebo treatment or a procedure.

For the time period beginning at treatment allocation/randomization through 90 days following cessation of treatment, or 30 days following cessation of treatment if the subject initiates new anticancer therapy, whichever is earlier, any ECI, or follow up to an ECI, whether or not related to Merck product, must be reported within 24 hours to the Sponsor and within 24 hours to Merck Global Safety.

Events of clinical interest for this trial include:

1. An overdose of Merck product, as defined in Section 7.2.1 - Definition of an Overdose for This Protocol and Reporting of Overdose to the Sponsor, that is not associated with clinical symptoms or abnormal laboratory results.
2. An elevated AST or ALT lab value that is greater than or equal to 3X the upper limit of normal and an elevated total bilirubin lab value that is greater than or equal to 2X the upper limit of normal and, at the same time, an alkaline phosphatase lab value that is less than 2X the upper limit of normal, as determined by way of protocol-specified laboratory testing or unscheduled laboratory testing. *

*Note: These criteria are based upon available regulatory guidance documents. The purpose of the criteria is to specify a threshold of abnormal hepatic tests that may require an additional evaluation for an underlying etiology.

20.7 Protocol-Specific Exceptions to Serious Adverse Event Reporting

Efficacy endpoints as outlined in this section will not be reported to Merck as described in Section 20.5- Immediate Reporting of Adverse Events to the Sponsor and to Merck, unless there is evidence suggesting a causal relationship between the drug and the event. Any such event will be submitted to the Sponsor within 24 hours and to Merck Global Safety within 2 working days either by electronic or paper media.

Specifically, the suspected/actual events covered in this exception include any event that is disease progression of the cancer under study.

The Sponsor will monitor un-blinded aggregated efficacy endpoint events and safety data to ensure the safety of the subjects in the trial. Any suspected endpoint which upon review is not progression

of the cancer under study will be forwarded to Merck Global Safety as a SAE within 2 working days of determination that the event is not progression of the cancer under study.

Hospitalization related to convenience (e.g. transportation issues etc.) will not be considered a SAE.

20.8 Evaluating Adverse Events

An investigator who is a qualified physician will evaluate all adverse events according to the NCI Common Terminology for Adverse Events (CTCAE), version 4.0. Any adverse event which changes CTCAE grade over the course of a given episode will have each change of grade recorded on the adverse event case report forms/worksheets.

All adverse events regardless of CTCAE grade must also be evaluated for seriousness.

Table 6 EVALUATING ADVERSE EVENTS: An investigator who is a qualified physician will evaluate all adverse events as to:

V4.0 CTCAE Grading	Grade 1	Mild; asymptomatic or mild symptoms; clinical or diagnostic observations only; intervention not indicated.
	Grade 2	Moderate; minimal, local or noninvasive intervention indicated; limiting age-appropriate instrumental ADL.
	Grade 3	Severe or medically significant but not immediately life-threatening; hospitalization or prolongation of hospitalization indicated; disabling; limiting self-care ADL.
	Grade 4	Life threatening consequences; urgent intervention indicated.
	Grade 5	Death related to AE
Seriousness	A serious adverse event is any adverse event occurring at any dose or during any use of Merck product that:	
	† Results in death ; or	
	† Is life threatening ; or places the subject, in the view of the investigator, at immediate risk of death from the event as it occurred (Note: This does not include an adverse event that, had it occurred in a more severe form, might have caused death.); or	
	† Results in a persistent or significant disability/incapacity (substantial disruption of one's ability to conduct normal life functions); or	
	† Results in or prolongs an existing inpatient hospitalization (hospitalization is defined as an inpatient admission, regardless of length of stay, even if the hospitalization is a precautionary measure for continued observation. (Note: Hospitalization [for an elective procedure] to treat a pre-existing condition that has not worsened is not a serious adverse event. A pre-existing condition is a clinical condition that is diagnosed prior to the use of a Merck product and is documented in the patient's medical history); or	
	† Is a congenital anomaly/birth defect (in offspring of subject taking the product regardless of time to diagnosis); or	
	Is a new cancer (that is not a condition of the study) (although not serious per ICH definition, is reportable to the Sponsor within 24 hours and to Merck within 2 working days to meet certain local requirements); or	
	Is an overdose (whether accidental or intentional). Any adverse event associated with an overdose is considered a serious adverse event for collection purposes. An overdose that is not associated with an adverse event is considered a non-serious event of clinical interest and must be reported within 24 hours to the Sponsor and to Merck within 2 working days.	
Other important medical events that may not result in death, not be life threatening, or not require hospitalization may be considered a serious adverse event when, based upon appropriate medical judgment, the event may jeopardize the subject and may require medical or surgical intervention to prevent one of the outcomes listed previously (designated above by a †).		

Duration	Record the start and stop dates of the adverse event. If less than 1 day, indicate the appropriate length of time and units	
Action taken	Did the adverse event cause Merck product to be discontinued?	
Relationship to Merck Product	Did Merck product cause the adverse event? The determination of the likelihood that Merck product caused the adverse event will be provided by an investigator who is a qualified physician. The investigator's signed/dated initials on the source document or worksheet that supports the causality noted on the AE form, ensures that a medically qualified assessment of causality was done. This initialed document must be retained for the required regulatory time frame. The criteria below are intended as reference guidelines to assist the investigator in assessing the likelihood of a relationship between the test drug and the adverse event based upon the available information. The following components are to be used to assess the relationship between Merck product and the AE; the greater the correlation with the components and their respective elements (in number and/or intensity), the more likely Merck product caused the adverse event (AE):	
	Exposure	Is there evidence that the subject was actually exposed to Merck product such as: reliable history, acceptable compliance assessment (pill count, diary, etc.), expected pharmacologic effect, or measurement of drug/metabolite in bodily specimen?
	Time Course	Did the AE follow in a reasonable temporal sequence from administration of Merck product? Is the time of onset of the AE compatible with a drug-induced effect (applies to trials with investigational medicinal product)?
	Likely Cause	Is the AE not reasonably explained by another etiology such as underlying disease, other drug(s)/vaccine(s), or other host or environmental factors

Relationship to Merck Product (continued)	The following components are to be used to assess the relationship between the test drug and the AE: (continued)	
	Dechallenge	Was Merck product discontinued or dose/exposure/frequency reduced? If yes, did the AE resolve or improve? If yes, this is a positive dechallenge. If no, this is a negative dechallenge. (Note: This criterion is not applicable if: (1) the AE resulted in death or permanent disability; (2) the AE resolved/improved despite continuation of the Sponser's product; or (3) the trial is a single-dose drug trial); or (4) Sponser's product(s) is/are only used one time.)
	Rechallenge	Was the subject re-exposed to Merck product in this study? If yes, did the AE recur or worsen?

		
If yes, this is a positive rechallenge. If no, this is a negative rechallenge. (Note: This criterion is not applicable if: (1) the initial AE resulted in death or permanent disability, or (2) the trial is a single-dose drug trial); or (3) Sponser's product(s) is/are used only one time).
 
NOTE: IF A RECHALLENGE IS PLANNED FOR AN ADVERSE EVENT WHICH WAS SERIOUS AND WHICH MAY HAVE BEEN CAUSED BY MERCK PRODUCT, OR IF REEXPOSURE TO MERCK PRODUCT POSES ADDITIONAL POTENTIAL SIGNIFICANT RISK TO THE SUBJECT, THEN THE RECHALLENGE MUST BE APPROVED IN ADVANCE BY THE SPONSER AS PER DOSE MODIFICATION GUIDELINES IN THE PROTOCOL.

	Consistency with Trial Treatment Profile	Is the clinical/pathological presentation of the AE consistent with previous knowledge regarding Merck product or drug class pharmacology or toxicology?
The assessment of relationship will be reported on the case report forms /worksheets by an investigator who is a qualified physician according to his/her best clinical judgment, including consideration of the above elements.		
Record one of the following	Use the following scale of criteria as guidance (not all criteria must be present to be indicative of Merck product relationship).	
Yes, there is a reasonable possibility of Merck product relationship.	There is evidence of exposure to Merck product. The temporal sequence of the AE onset relative to the administration of Merck product is reasonable. The AE is more likely explained by Merck product than by another cause.	
No, there is not a reasonable possibility of Merck product relationship	Subject did not receive the Merck product OR temporal sequence of the AE onset relative to administration of Merck product is not reasonable OR the AE is more likely explained by another cause than the Merck product. (Also entered for a subject with overdose without an associated AE.)	

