- 1) We will estimate the rate of objective response rate for the protocol treatment. The definition of objective response will be measured by RECIST 1.1. The objective response rate (ORR=CR+PR) along with its 95% exact confidence interval will be estimated.

- 2) We will evaluate disease-free survival and patterns of metastases after protocol treatment. Disease-free survival (DFS) is defined as the time from surgical resection to disease recurrence (first disease recurrence or death, whichever comes first) after surgery. The Kaplan-Meier estimator will be used to estimate median DFS and its confidence interval. The frequencies of metastases by site will be tabulated.
- 3) Blood based biomarkers will be evaluated for the changes before and after the protocol treatment. The association of the baseline value and the changes of these biomarkers with clinical outcomes, such as objective response, overall survival and disease free survival, will be evaluated using logistics regression and Cox models.
- 4) We will determine the percentage of patients with “detectable” (percentage of $\geq 0.05\%$ with each value also being at least twice that of the background unstimulated control value) tumor infiltrating lymphocytes (TILs) after protocol treatment. The percentage of patients with TILs for patients who have surgical resection and its exact confidence interval will also be estimated.
- 5) We will evaluate whether presence, quantity or quality of detectable TILs is associated with pathologic response to neoadjuvant therapy. A Fisher exact test will be used to evaluate the association of both the presence and the quality of TILs with pathologic tumor response to neoadjuvant therapy. A Wilcoxon rank sum test will be used to test the association of the quantity of TILs and pathologic response to neoadjuvant therapy.
- 6) Treatment-related adverse events will be summarized by type and grade.
- 7) The proportion of patients with detectable circulating T cells specific against TAA after the protocol treatment will be estimated and its confidence interval will be provided. An exact binominal test will be used to test the increase in the proportion of patients with detectable circulating T cells specific against TAA after the protocol treatment relative to baseline.
- 8) Estimate the rate of pathologic response for neoadjuvant pembrolizumab in early stage NSCLC. The pathologic response rate along with its 95% exact confidence interval will be estimated.

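### The only planned adverse-event tabulation is limited to treatment-related events, and the protocol's only relatedness scale lets some events be coded either way

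*Combined protocol and SAP*

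**What the plan says.** Section 27.1, secondary objective 6, reads "Treatment-related adverse events will be summarized by type and grade"; section 4.2 carries the same objective. No tabulation regardless of cause is named in either place, and neither defines treatment-related. Under adverse event monitoring, 27.1 also states that in this design events are hard to assign reliably to pembrolizumab, the operation or something else.

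The only scale for relatedness is Table 6 in 20.8. It is introduced with "Use the following scale of criteria as guidance (not all criteria must be present to be indicative of Merck product relationship", and the final decision is left to the physician investigator's judgment. The Yes row lists three criteria: "There is evidence of exposure to Merck product"; "The temporal sequence of the AE onset relative to the administration of Merck product is reasonable"; and the product being a likelier explanation than any other cause. The No row is met if the product was not received, or if the timing "is not reasonable OR the AE is more likely explained by another cause than the Merck product".

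Section 20.2 has all adverse events reported from treatment allocation through 30 days after treatment ends, whatever their attribution. Section 20.0 treats every patient with at least one dose as evaluable for safety.

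**The concern.** A related-only table is only as reproducible as the relatedness decision behind it. Here the plan itself says the decision is hard, and the scale gives conflicting instructions for one kind of event: exposure certain, timing plausible, another cause likelier. The design makes room for such events, because surgery and, for some patients, chemotherapy or radiation fall between the two pembrolizumab courses.

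The trial has several institutions (3.2) and no control arm. If two sites resolve the conflict differently, their related-event rates differ for a reason unrelated to toxicity. A reader who sees only the filtered counts cannot detect this, and there is no control rate to compare them with.

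**Working it through.** The plan gives no figure to reproduce, so the check is logical.

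**1. Inputs.** From Table 6: exposure (yes or no), timing (reasonable or not), likelier cause (product, equal, other). That gives 2 × 2 × 3 = 12 combinations.

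**2. Rules.** No applies if exposure is absent, or timing is unreasonable, or another cause is likelier. Yes is tried in two ways: (a) all three criteria required; (b) any two of the three sufficient. Reading (b) is an assumption about what the introductory line allows; the protocol gives no number.

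**3. Result.** The combinations that matter are:

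| Exposure | Timing reasonable | Likelier cause | Yes, reading (a) | Yes, reading (b) | No |
|---|---|---|---|---|---|
| yes | yes | product | met | met | not met |
| yes | yes | equal | not met | met | not met |
| yes | yes | other | not met | met | met |
| yes | no | product | not met | met | met |
| no | yes | product | not met | met | met |

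The other seven combinations meet No only. Under (a) no combination fits both rows, but the tie (exposed, plausible timing, causes equally likely) fits neither. Under (b) the tie is Yes, and three combinations fit both rows. The third row of the table is the one of practical interest.

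**4. Source of the overlap.** The two rows read alone are opposites on likelier cause. The conflict arises only when the introductory line, "not all criteria must be present to be indicative of Merck product relationship", is applied to them. Requiring all three criteria removes the overlap but sets that line aside.

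**5. Effect on the table.** For a given event type, let a be the number of patients with a clearly related event and m the number whose only such event is ambiguous. The related-only count lies between a and a + m, depending on the reading. A count regardless of cause is the same under both. The documents give neither a nor m. Purely as an illustration with assumed rates: with 30 evaluable patients and a clear rate of 10%, a = 30 × 0.10 = 3.0. If a further 5%, 10% or 20% are ambiguous, the upper count is 30 × 0.15 = 4.5, 30 × 0.20 = 6.0 or 30 × 0.30 = 9.0.

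**6. Direction.** Let q be the chance that pembrolizumab caused an ambiguous event, with an assumed Beta(1, b) distribution, so that E[q] = 1/(1 + b) and P(q ≥ 0.5) = 0.5^b. Coding No whenever another cause is likelier gives a related count, relative to the true number of drug-caused events, of (1 + b) × 0.5^b: 1.00, 0.75 and 0.50 for b = 1, 2 and 3. Coding every such event Yes gives 1/E[q] = 2, 3 and 4 times the true number. Strict coding is never higher than lenient coding, but which one is nearer the truth depends on the assumed distribution.

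**The case against.** The strongest reply is that Table 6 is not an algorithm. It calls itself guidance, leaves the decision to clinical judgment, and offers dechallenge, rechallenge and consistency with the known profile to help settle doubtful cases. If all three Yes criteria are required, there is no overlap at all. This narrows the point: the conflict comes from one line. It does not remove it, because judgment exercised against two inconsistent definitions can still differ between sites.

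It is also fair that item 6 is not the whole safety evaluation. Section 27.1 rests its safety and feasibility verdict on two other criteria, all toxicity patterns go to the safety oversight committee, and 20.0 bases safety assessment on adverse event reports generally. Nor is item 6 expressly tied to Table 6. That stands, but no other relatedness scale is offered and no other adverse-event tabulation is named.

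A reader might infer more than the documents support:

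- That toxicity will be understated. Step 6 of the working shows that strict coding need not understate, and that lenient coding can overstate.
- That the swing has a known size. Any multiple comes from an assumed distribution.
- That ambiguous events will be common. Adjuvant chemotherapy and radiation go only to selected patients, Appendix A schedules no adverse-event assessment during them, and no frequency is given.
- That one episode will be counted several times because an event that changes grade "will have each change of grade recorded on the adverse event case report forms/worksheets". That is a recording rule; nothing says each change is tabulated separately.
- That serious-event reporting and follow-up depend on the flag. Within the reporting window in 20.5.1, serious events are reported whether or not related; the flag matters for later ones "considered by an investigator who is a qualified physician to be related to Merck product". Section 9.8.5 limits follow-up to related events above grade 1, but 20.2 asks for every attempt to follow non-serious events, 20.5.1 requires follow-up of all serious ones, and 9.6 applies no relatedness filter.

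**Conclusion.** The point holds in a limited form. The single adverse-event tabulation named in 27.1 filters on attribution that the plan calls difficult, and Table 6 lets a treated patient's event with plausible timing and a likelier competing cause be coded either way. Related-only counts can therefore differ between sites and readers.

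This rests on reading the introductory line in Table 6 as allowing exposure plus timing to suffice for Yes, and on Table 6 being the source of the term treatment-related, which the documents imply but do not state. The direction and size of any difference cannot be derived from the documents; the counts in step 5 of the working are illustrations, not estimates. The data needed to remove the dependence are already being collected, so this is an inexpensive reporting gap and not a flaw in safety surveillance.

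**What to change.** 1. In 27.1 item 6 and 4.2 item 6, plan a table of all adverse events from the first dose of pembrolizumab regardless of attribution, over the collection window in 20.2, among all patients who received at least one dose. Count each patient once per event type at worst grade. Show the related subset beside it, and state whether related means related to pembrolizumab or to any protocol treatment.

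2. In Table 6, reconcile the introductory line with the Yes and No rows so that every event, including one with equally likely causes, falls in exactly one category. Which causality convention to adopt is the sponsor's choice. Counting any possible contribution as Yes would avoid the overlap but could overstate related events, so it should not be treated as the automatic correction.

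The cost is one more table from existing data and a wording change in the statistical section and Table 6, communicated to the sites. No new data, visits or patients are needed.
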